6.11. Analysis Methodology for Primary and Major Secondary Outcomes

The primary endpoint for this study is the proportion of patients achieving treatment success, defined as achieving sPGA of Genitalia (0,1) at Week 12 (end of the Blinded Treatment Period) and remaining on the initially randomized treatment (i.e. the effect attributable to the originally randomized treatment, ixekizumab Q2W). With this estimand any patient who discontinues treatment prior to Week 12 is considered a treatment failure through the use of the NRI. The numeric result for treatment success/failure is identical to NRI but interpreted differently and has different consequences for missing data. With NRI, as the acronym implies, there is explicit imputation of missing sPGA of Genitalia (0,1) outcomes. With treatment success/failure, discontinuation of study medication is considered a treatment failure because if patients cannot adhere to the medication they will not have sustained benefit from it. Therefore, every patient will have an observation for treatment success/failure and placebo, at the primary time point of Week 12 in all randomized patients) and there will be no missing data for this estimand and hence inferences will not depend on missing data assumptions. These attributes also apply to other endpoints involving use of NRI.

The major secondary endpoints for this study are

1. The proportion of patients achieving an overall sPGA (0,1) at Week 12.
2. The proportion of patients with at least a 3 point improvement in genital psoriasis itch NRS within the GPSS at Week 12. This will be calculated for patients who had baseline score of at least 3.
3. The proportion of patients achieved a SFQ Item #2 score of 0 or 1 at Week 12. This will be calculated for patients who had baseline score of at least 2.

The primary analysis method for the primary endpoint will be based on a logistic regression analysis with treatment and BSA category as factors in the model and compare the ixekizumab Q2W dosing versus placebo at Week 12 (Visit 7) using the ITT Population (Section 6.1.3).

The primary analysis method for the major secondary endpoint #1-3 will be based on a logistic regression analysis with treatment and BSA category as factors in the model and compare the ixekizumab Q2W dosing versus placebo at Week 12 (Visit 7) using the ITT population (Section 6.1.3).

The primary endpoint will be tested at 2-sided $\alpha = 0.05$. If the test for primary endpoint is significant, then the test for the major secondary endpoint #1 will be performed. If the test for major secondary endpoint #1 is significant, then the test for major secondary endpoint #2 will be performed. Similarly, the test for major secondary endpoint #3 will be performed only if all prior tests are significant. If a test is not significant, all subsequent tests will be considered not significant.

Other secondary and tertiary analyses will be performed on the primary and major secondary efficacy endpoints as detailed in [Table RHBQ.6.5](#).

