9.2. General Statistical Considerations

Statistical analysis of this study will be the responsibility of Eli Lilly and Company.

Categorical data for baseline variables will be summarized as frequency counts and percentages. Continuous data for baseline variables will be summarized in using the mean, standard deviation, minimum, maximum, median, and number of observations.

Any change to the data analysis methods described in the protocol will require an amendment ONLY if it changes a principal feature of the protocol. Any other change to the data analysis methods described in the protocol, and the justification for making the change, will be described in the clinical study report (CSR). Additional exploratory analyses of the data will be conducted as deemed appropriate.

Complete details of the planned analyses will be documented in the statistical analysis plan (SAP).

General Considerations for Analyses during Period 2 (Blinded Treatment Period)

Comparisons of ixekizumab Q2W dosing versus placebo will be performed for all outcome variables in Period 2. Baseline will be defined as the last available value before the first injection of the investigational product for both efficacy and safety analyses. In most cases, this will be the measurement recorded at Week 0 (Visit 2). For efficacy measures, if the patient does not take any injection, the last available value on or prior to randomization date will be used. Change from baseline at a particular visit will be calculated as the value at that visit minus the baseline value. For safety analyses using a baseline period, the baseline period is defined as the time from Visit 1 to the date/time of the first injection.

For outcome measures that are not collected at each postbaseline visit, data may exist at visits where the outcome measure was not scheduled to be collected, due to ETVs. In these situations,

data from the ETVs that does not correspond to the planned collection schedule will be excluded from any mixed-effects models for repeated measures (MMRM) analysis. However, the data will still be used in other analyses, including shift analyses, change from baseline analyses using last observation carried forward (LOCF) imputation method, and other categorical analyses.

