9.5. Primary and Secondary Analyses

9.5.1. Primary Analyses

- Categorical
 - Treatment comparisons of categorical efficacy and health outcome variables will be performed using a logistic regression model with treatment and BSA category as factors, using the NRI method.
- Continuous
 - The primary analyses for all continuous efficacy and health outcome variables will be performed using MMRM. The model will include treatment, baseline BSA category, baseline value, visit, treatment-by-visit interaction, and baseline-by-visit interaction as fixed factors. The covariance structure to model the within-patient errors will be unstructured. If the unstructured covariance matrix results in a lack of convergence, the heterogeneous Toeplitz covariance structure, followed by the heterogeneous autoregressive covariance structure will

be used. The Kenward-Roger method will be used to estimate the denominator degrees of freedom. Type III tests for the least-square (LS) means will be used for the statistical comparison; the 95% confidence interval (CI) will also be reported. Treatment group comparisons at all visits up to Week 12 will be tested. If the unstructured covariance matrix results in a lack of convergence, the heterogeneous Toeplitz covariance structure, followed by the heterogeneous autoregressive covariance structure, followed by the compound symmetry will be used. This order is specified according to a decreasing number of covariance parameters in the structure.

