6.1.3. Analysis Methods

6.1.3.1. Primary Analysis Method

- **Categorical**
 - Treatment comparisons of all categorical efficacy and health outcome variables will be performed using a logistic regression model with treatment and BSA category (<10% vs ≥10% BSA at baseline) as factors, using the NRI method. The odds ratios (OR) and the corresponding 95% CIs, will be reported.
- **Continuous**
 - The primary analyses for all continuous efficacy and health outcome variables will be performed using MMRM. The model will include treatment, baseline BSA category, baseline value, visit, treatment-by-visit interaction, and baseline-by-visit interaction as fixed factors. The covariance structure to model the within-patient errors will be unstructured. If the unstructured covariance matrix results in a lack of convergence, the heterogeneous Toeplitz covariance structure, followed by the heterogeneous autoregressive covariance structure, followed by the compound symmetry will be used. The Kenward-Roger method will be used to estimate the denominator degrees of freedom. Type III tests for the least-square (LS) means will be used for the statistical comparison; the 95% CI will also be reported. Treatment group comparisons at all visits up to Week 12 will be tested. This order is specified according to a decreasing number of covariance parameters in the structure.

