6.1.3.2. Secondary Analysis Method

- Categorical
 - Secondary analysis on the categorical efficacy and health outcome variables will be conducted using a Fisher's exact test.
 - A categorical, pseudo-likelihood-based MMRM analysis for categorical repeated measures will be performed only for the primary endpoint of the sPGA of Genitalia (0,1) as analysis for estimating the percentage of patients achieving response across post-baseline visits in the Blinded Treatment Period. The model will include treatment, baseline BSA category, baseline value, visit, treatment-by-visit interaction, and baseline-by-visit interaction as fixed factors. The binomial distribution and the logit link function will be used. The restricted maximum likelihood (REML) will be used. An unstructured covariance matrix will be used to model the within-patient variance-covariance errors. The Kenward-Roger approximation will be used to estimate the denominator degrees of freedom. The Newton-Raphson with ridging optimization technique will be used to aid with convergence. The probability of response, the corresponding 2-sided 95% CI, and the p-value for the treatment group comparisons at Week 12 (Visit 7) and all other post-baseline visits will be reported.

If the unstructured covariance matrix results in a lack of convergence, the heterogeneous Toeplitz covariance structure, followed by the heterogeneous autoregressive covariance structure, followed by the compound symmetry will be used. This order is specified according to a decreasing number of covariance parameters in the structure. The sandwich estimator (Diggle et al. 1994) for the covariance estimation will be used by specifying the EMPIRICAL option in SAS PROC MIXED. When the sandwich estimation is used, the Kenward-Roger approximation for denominator degrees of freedom cannot be used. Instead, the DDFM= BETWITHIN option will be used to estimate denominator degrees of freedom.

- Treatment differences (Absolute Risk Reductions [ARR]), Relative Risks (RR), Numbers Needed to Treat (NNT) estimates and their corresponding 95% CIs, will also be reported.
- Continuous

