6.2. Adjustments for Covariates

The randomization at the beginning of the Blinded Treatment Period (Period 2) is stratified by **baseline BSA category** (<10% vs ≥10% BSA at baseline). Unless otherwise specified, all efficacy and health outcome analyses during Period 2 will include baseline BSA category in the analysis model.

In general, when an MMRM or Categorical MMRM is to be used for analyses, baseline value and baseline-by-visit interactions will be included as covariates; when an ANCOVA is to be used for analyses, baseline value will be included as a covariate.

The OBSMARGINS/OM option will be used in the LSMEANS statement to account for imbalance in the BSA categories as we expect to enroll patients in approximately 40:60 ratio from the BSA <10% and ≥10% categories.

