6.4. Multiple Comparisons/Multiplicity

A multiple testing strategy for the primary and the major secondary endpoint will be implemented to control the family-wise Type I error rate at a 2-sided α level of 0.05. The primary and major secondary endpoints will be sequentially tested in the following order to compare ixekizumab Q2W versus placebo, using the primary analysis method specified in Section 6.1.3.1.

1. Primary – Proportion of patients achieving sPGA of Genitalia (0,1) at Week 12
2. Major Secondary #1 – Proportion of patients achieving an overall sPGA (0,1) at Week 12
3. Major Secondary #2 – Proportion of patients with at least a 3 point improvement in genital psoriasis itch Numeric Rating Scale (NRS) within the GPSS at Week 12. This will be calculated for patients who had baseline score of at least 3.
4. Major Secondary #3 – Proportion of patients achieving a SFQ Item #2 score of 0 or 1, at Week 12. This will be calculated for patients who had baseline score of at least 2.

The primary endpoint will be tested at 2-sided $\alpha = 0.05$. If the test for primary endpoint is significant, then the test for the major secondary endpoint #1 will be performed. If the test for major secondary endpoint #1 is significant, then the test for major secondary endpoint #2 will be performed. If a test is not significant, all subsequent tests will be considered not significant.

There will be no adjustment for multiple comparisons for any other analyses.

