		3-point improvement in Genital Psoriasis Itch NRS	
First calculate
 
Change from baseline $= \text{Observed Genital Psoriasis Itch NRS score} - \text{Baseline Genital Psoriasis Itch NRS score}$
 
If change from baseline is less than or equal to -3, then the patient has experienced a 3-point improvement. If change from baseline is greater than -3, then the patient has not experienced a 3-point improvement.
	Missing if either observed or baseline Genital Psoriasis Itch NRS score is missing

Measure	Description	Variable	Derivation	Imputation Approach if Components are Missing

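### Adding the baseline score to the itch (Test 3) and SFQ Item 2 (Test 4) responder models could recover some power at little cost

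*SAP*

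**What the plan says.** SAP 6.11 fixes the model for Tests 2 to 4: "The primary analysis method for the major secondary endpoint #1-3 will be based on a logistic regression analysis with treatment and BSA category as factors". This follows the general rule in SAP 6.1.3.1, "Treatment comparisons of all categorical efficacy and health outcome variables will be performed using a logistic regression model with treatment and BSA category", and Protocol 9.5.1, "Treatment comparisons of categorical efficacy and health outcome variables will be performed using a logistic regression model with treatment and BSA category as factors".

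Elsewhere the SAP does adjust for baseline. SAP 6.2 says that "when an MMRM or Categorical MMRM is to be used for analyses, baseline value and baseline-by-visit interactions will be included as covariates", and it gives ANCOVA the same rule. It does not mention logistic regression. The one responder model that contains the baseline value is the categorical MMRM in SAP 6.1.3.2, which "will be performed only for the primary endpoint of the sPGA of Genitalia (0,1").

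For the itch and SFQ Item 2 responder endpoints, Table RHBQ.6.5 lists logistic regression with NRI and Fisher's exact test with NRI, plus a Kaplan-Meier analysis of time to itch response. Itch also has MMRM and ANCOVA analyses of mean change, outside the alpha-controlled sequence. SFQ Item 2 has no baseline-adjusted treatment comparison.

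Test 3 is restricted by baseline: "This will be calculated for patients who had baseline score of at least 3". Test 4 requires a baseline of at least 2. Response differs in kind between the two. For itch it is a change score: "If change from baseline is less than or equal to -3, then the patient has experienced a 3-point improvement". For SFQ Item 2 it is a Week 12 score of 0 or 1.

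**The concern.** Tests 3 and 4 are the last two alpha-controlled steps, and if Test 3 fails, Test 4 fails automatically. Both run in baseline-restricted subsets for which no size is planned. Randomisation is stratified only by BSA, so chance imbalance in baseline score within these subsets is possible and the planned models ignore it.

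For itch, the definition itself suggests that baseline predicts response. A patient entering at 3 must reach 0 to respond, which is a 100% reduction. A patient entering at 8 need only reach 5, a 37.5% reduction. Where a covariate predicts a binary outcome, leaving it out of a logistic model costs some power for the treatment comparison.

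The link is less obvious for SFQ Item 2. Its baseline takes only three values (2, 3 or 4), and the target is fixed and not a change.

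**Working it through.** **1. The plan's own power figure.** The inputs in SAP 5.3 are 73 per group, 2% versus 20%, and a two-sided Fisher's exact test at 0.05. Exact enumeration gives 94.7% and the normal approximation 94.3%, so the stated 94% reproduces. It concerns DLQI Item 9 in all 146 patients. The documents contain no power figure for Test 3 or Test 4.

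**2. The two models compared.**

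- Planned: logit P(response) = b0 + b1·treatment + b2·BSA category
- With baseline: the same, plus b3·baseline score

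Everything below is assumed except the two-sided 0.05 level (SAP 6.4) and the 40:60 BSA mix (SAP 6.2). Both models were fitted to each simulated trial.

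**3. Logistic data model** (2,000 trials per setting, likelihood-ratio test). Here logit p = a(arm) + ln(OR)·(baseline − mean)/SD, with a(arm) solved to give the stated response rates. Itch baseline is uniform on 3 to 9.5. SFQ Item 2 baseline is 2, 3 or 4 with probabilities 0.40, 0.35 and 0.25. The direction of the association is reversed for SFQ.

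| Endpoint and rates | OR per baseline SD | Per arm | Power, planned → with baseline |
|---|---|---|---|
| Itch, 55% vs 35% | 1.0 to 1.5 | 40 or 55 | change of −0.1 to +1.6 points |
| Itch, 55% vs 35% | 2.5 | 40 | 45.7 → 52.0% |
| Itch, 55% vs 35% | 2.5 | 55 | 54.9 → 63.5% |
| Itch, 60% vs 20% | 1.0 to 2.5 | 40 or 55 | change of −0.1 to +1.5 points |
| SFQ, 60% vs 40% | 1.0 to 1.5 | 30 or 40 | change of −0.9 to +1.6 points |
| SFQ, 60% vs 40% | 2.5 | 30 | 35.5 → 41.0% |
| SFQ, 60% vs 40% | 2.5 | 40 | 45.6 → 51.6% |
| SFQ, 75% vs 25% | 1.0 to 2.5 | 30 or 40 | change of −0.2 to +0.9 points |

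A repeat run at OR 2.5 gave 56.7 → 64.0% (itch, 55 per arm, 55% vs 35%) and 45.6 → 52.2% (SFQ, 40 per arm, 60% vs 40%).

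**4. Proportional-improvement model, itch only** (3,000 trials per setting). Each patient improves by a fraction of baseline with SD 0.30, and responds if fraction × baseline ≥ 3. With a mean fraction of 0.55 and a normal distribution, the response probability is 1 − Φ((3/3 − 0.55)/0.30) = 1 − Φ(1.50) = 6.7% at baseline 3, and 1 − Φ((3/8 − 0.55)/0.30) = 1 − Φ(−0.58) = 72% at baseline 8. Baseline is therefore strongly prognostic by construction.

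| Response rates (mean fractions) | 40 per arm | 55 per arm |
|---|---|---|
| 53% vs 36% (0.55 vs 0.40) | 33.6 → 38.7% | 43.3 → 48.7% |
| 58% vs 34% (0.60 vs 0.38) | 60.8 → 67.9% | 74.9 → 81.8% |
| 64% vs 29% (0.65 vs 0.33) | 90.7 → 94.6% | 96.5 → 98.7% |
| 74% vs 21% (0.75 vs 0.25) | 99.8 → 99.9% | 100 → 100% |

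**5. A second set of assumptions** (2,000 trials per setting, Wald test). Total N was 146, 110 or 74; placebo versus active rates were 10% vs 30%, 20% vs 45% or 30% vs 55%. Itch baseline was uniform on 3 to 10, and SFQ baseline uniform on 2, 3 and 4.

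| OR per baseline SD | Gain in power |
|---|---|
| 1.0 | within ±0.8 points |
| 0.67 | about +0.5 to +2 points |
| 0.5 | about +1 to +6 points |
| 0.33 | about +4 to +10 points |

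For example, itch with N = 110, 20% vs 45% and OR 0.5 goes from 82.1 to 85.6%. SFQ with N = 74, 30% vs 55% and OR 0.33 goes from 56.0 to 65.9%.

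**6. Type I error.** With the likelihood-ratio test it was 4.8 to 6.2% for the planned model and 4.6 to 6.4% with baseline (Monte Carlo SE about 0.5 points at 2,000 trials). With the Wald test and 4,000 trials it was 4.0 to 5.7% planned and 4.3 to 5.1% with baseline.

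**The case against.** The strongest reply is that the benefit rests wholly on assumptions, and that the larger gains need a very strong association. An odds ratio of 2.5 per SD implies:

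- Itch: SD = 6.5/√12 = 1.88, so the odds differ by 2.5^(6.5/1.88), about 24-fold, between baseline 3 and 9.5.
- SFQ Item 2: SD 0.79, so the odds differ by 2.5^(1/0.79), about 3.2-fold, per level and about 10-fold between 2 and 4.

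The proportional-improvement model builds the association in. None of the simulations represents discontinuations scored as failures, which could weaken it.

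The documents also hint at large effects: more than 80% PASI 75 in earlier Phase 3 trials, and a design built on 2% versus 20%. These are other endpoints, but with large effects power is near its ceiling under either model. At OR 2.5, itch at 60% vs 20% with 40 per arm went from 96.5 to 98.5% in 3,000 trials. Tests 3 and 4 are also reached only after Tests 1 and 2 succeed, which the simulations ignore.

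All of this limits the size of the gain and stands to that extent. So does the weaker case for SFQ Item 2, where a single linear term over three ordinal levels is itself an assumption.

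Three further points carry less weight. The change is not literally free, because the odds ratio becomes conditional on baseline and Tests 3 and 4 would no longer share one model with Tests 1 and 2. The baseline-adjusted mean-change analyses of itch do exist, but they do not test the responder endpoint. The 6.4% type I error is a maximum over several settings and reflects the likelihood-ratio test more than the covariate: the planned model reached 6.2% on the same basis, and the Wald test stayed close to 5%.

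**Conclusion.** The point holds as an optional efficiency gain. The planned models are valid and consistent with the protocol. They leave out a covariate that is already measured, that the SAP uses in its MMRM, categorical MMRM and ANCOVA models, and that is plausibly prognostic for itch by definition.

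The expected gain is about 0 to 2 percentage points of power if prognosis is weak or effects are large, and about 5 to 9 points if prognosis is strong and effects are moderate. The most extreme association tried (OR 0.33 per SD) gave up to about 10. No material loss of power appeared in any setting. Which end of the range applies depends on rates, subset sizes and prognostic strength that the documents do not give. Confidence in the size is moderate at best, and lower for SFQ Item 2.

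**What to change.** Before the Week 12 lock and unblinding:

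- Add baseline itch NRS, as a continuous term, to the Test 3 logistic model.
- Add baseline SFQ Item 2, as one linear term, to the Test 4 model.
- Keep BSA category in both, and report the planned treatment and BSA model as a sensitivity analysis.
- State which test of the treatment term gives the p-value, since the SAP names none. In these simulations the Wald test was closer to the nominal level.
- Leave Tests 1 and 2 unchanged.

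The cost is text in SAP 6.1.3.1, 6.2, 6.4, 6.11 and Table RHBQ.6.5, and consistency with Protocol 9.5.1. Protocol 9.2 requires an amendment only if a principal feature changes. For lesser changes an entry in the CSR is enough: "Any other change to the data analysis methods described in the protocol, and the justification for making the change, will be described" there. The sponsor should record which of these applies to a confirmatory model.

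No new data are needed and no further patients are excluded, because each analysis set is already defined by a non-missing baseline score. The adjusted odds ratio should be labelled as conditional on baseline. The risk differences, relative risks and numbers needed to treat already planned in SAP 6.1.3.2 remain available for a marginal reading.

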6.12. Other Secondary Efficacy Outcomes and Analysis methodology

There will be no adjustment for multiple comparisons for the other secondary efficacy outcomes. The other secondary endpoints are defined in Section 4.3. The analysis methods and corresponding populations are described in [Table RHBQ.6.5](#).

6.13. Health Outcomes/Quality of Life Analyses

The health outcomes and quality of life measures for this study are:

- GPSS
- GPSIS
- SFQ
- Touch avoidance
- PatGA-Genital
- DLQI
- SF-36: MCS and PCS and individual domains
- CAPP genital sub-index

These measures are defined in [Table RHBQ.6.4](#). The analysis methods and corresponding populations are described in [Table RHBQ.6.5](#).

The psychometric analyses of the diary endpoints, including GPSS, GPSIS and SFQ, are outlined in Section [6.20.1](#).

